12.6.3 Exploratory Analysis

12.6.3.1 Questionnaires

12.6.3.1.1 Urge-to-Smoke Questionnaire of Smoking Urges Brief

The QSU-brief will be administered daily from Days -1 to 5. The baseline will be the last assessment prior to 06:29 AM on Day 1.

All summaries, profiles and analysis will be presented for the THS 2.2, CC and SA arms.

The change from baseline will be calculated for the total score and the two domain scores (relief and reward). The total score and two domain scores, along with the change from baseline will be summarized. The answers to the individual questions, along with the domain scores, total scores and changes from baseline will be listed.

The profiles of the raw means from baseline to Day 5 for the total score and two domain scores will be produced.

The analysis will compare each post baseline timepoint in the domain and total scores. A repeated measures ANCOVA model will be used with terms for baseline QSU-BRIEF score, sex, average daily CC consumption over the last 4 weeks as reported during screening, product, timepoint, and the interaction between product and timepoint. No adjustment will be made for multiple comparisons.

The SAS code to be used is shown below:

```
Proc mixed data=_data_ ;  
Class product sex cigarette_cons time_point ;  
Model reduction = base_QSU sex cigarette_cons product  
product*time_point ;  
Repeated time_point / subject=subject type=un ;  
Lsmean product / diff alpha=0.05 cl ;  
Run ;
```

LS means for each product along with the difference (THS 2.2 - CC) and (THS 2.2 – SA) with 95% CI will be presented in the tables. The SAS code above will also be amended appropriately to obtain the right comparisons.

All figures, summaries and analyses will be performed on the FAS.

The data will be presented in the below outputs, the TFL number refers to the TFL number in the accompanying TFL shell document:

TFL number	Title
FIGURES	
15.1.2.33	QSU-brief Factors and Total Scores Arithmetic Mean and 95% CI– FAS
15.1.2.34	QSU-brief Factors and Total Scores Arithmetic Least Squares Mean Differences and 95% CI – FAS
TABLES	
15.2.4.48	Descriptive Statistics of QSU-brief Factors and Total Scores – FAS
15.2.4.49	Analysis of QSU-brief Factors and Total Scores – FAS
LISTINGS	
15.3.6.11	Listing of QSU-brief Questionnaire Results and Changes from Baseline

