7 DERIVED AND COMPUTED VARIABLES

Mean change from baseline (baseline is defined in Section 12.1.4 “Definitions for Statistical Data Analysis”) is the mean of all individual subjects’ change from baseline values. Each individual change from baseline will be calculated by subtracting the individual subject’s baseline value from the value at the timepoint. The individual subject’s change from baseline values will be used to calculate the mean change from baseline.

Mean percent change from baseline is the mean of all individual subjects’ percent change from baseline values. Each percent change from baseline will be calculated by subtracting the individual subject’s baseline value from the value at the desired timepoint and then

dividing this calculated value by the individual subject's baseline value and multiplying by 100. These individual subjects' percent changes from baseline values will be used to calculate the mean percent change from baseline.

When the baseline value is 0, 1 will be used in the denominator for calculating the percent change from baseline.

The QT interval corrected using Bazett's formula (QTcB) will be calculated as follows:

$$QTcB = \frac{QT}{\sqrt{\left(\frac{60}{HR}\right)}}$$

The QT interval corrected using Fridericia's formula (QTcF) will be calculated as follows:

$$QTcF = \frac{QT}{\sqrt[3]{\left(\frac{60}{HR}\right)}}$$

Reported BMI will be calculated at site from the body weight and height using the following formula:

$$BMI = \frac{\text{weight in kilograms}}{\text{height in meters}^2} \quad (\text{kg/m}^2)$$

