9 CHANGES FROM THE PROTOCOL SPECIFIED STATISTICAL ANALYSIS

- Shift tables for safety endpoints will not be produced for this study, the relevant information will be provided in listings.
- Statistical analysis for blood COHb (%) and exhaled CO (ppm) measurements and the QSU-brief questionnaire data, MNWS questionnaire data and the MCEQ questionnaire data will be performed including interaction terms for product and time point to enable least square means to be calculated at each time point in order to explore the pattern of the THS 2.2 effect over time. The main comparison between products will be the comparison over all time points.
- The second exploratory objective (“To evaluate in smokers switching from CC to THS 2.2, smokers continuing smoking CC and smokers switching from CC to SA the relationship between:

- Primary and secondary BoExp and NEQ
 - Selected risk markers and, primary and secondary BoExp, and NEQ
- will now only investigate:

- 1) The relationship between primary and secondary BoExp and NEQ, which will be reported in a separate report.
 - 2) The relationship between risk markers and NEQ, which will be reported in the CSR.
- The term “adjusted to creatinine” has been replaced by “adjusted for creatinine” in all relevant endpoints and analyses.

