12.6.3.1.2 Modified Cigarette Evaluation Questionnaire

The MCEQ will be administered daily from Days -1 to 5. The baseline will be the last assessment prior to 06:29 AM on Day 1.

All summaries, profiles and analysis will be presented for the THS 2.2 and CC only. The MCEQ is not captured for the SA arm.

The change from baseline will be calculated for the five domain scores. The domain scores, along with the change from baseline will be summarized. The answers to the individual questions, along with the domain scores and changes from baseline will be listed.

The profiles of the raw means from baseline to Day 5 for the five subscale scores will be produced.

The analysis will compare each post baseline timepoint in the subscales. A repeated measures ANOVA model will be used with terms for baseline MCEQ score, sex, average daily CC consumption over the last 4 weeks as reported during screening, product, time-point, and the interaction between product and time-point. No adjustment will be made for multiple comparisons.

The SAS code will be the same as described in Section 12.6.3.1.1 “Urge-to-Smoke Questionnaire of Smoking Urges Brief”.

LS means for each product along with the difference (THS 2.2 - CC) with 95% CI will be presented in the tables.

All figures, summaries and analyses will be performed on the FAS.

The data will be presented in the below outputs, the TFL number refers to the TFL number in the accompanying TFL shell document:

TFL number	Title
FIGURES	
15.1.2.38	MCEQ Subscales Arithmetic Mean and 95% CI– FAS
15.1.2.39	MCEQ Subscales Arithmetic Least Squares Mean Differences and 95% CI – FAS
TABLES	
15.2.4.52	Descriptive Statistics of MCEQ Subscales – FAS
15.2.4.53	Analysis of MCEQ Subscales – FAS
LISTINGS	
15.3.6.13	Listing of MCEQ Questionnaire Results and Changes from Baseline

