12.6.3.1.3 Minnesota Nicotine Withdrawal Questionnaire

The MNWS will be administered daily from Days 0 to 6 for the assessment of Day-1 to Day 5 as it is a 24-hour recall questionnaire. The baseline will be the last assessment prior to 06:29 AM on Day 1.

All summaries, profiles and analysis will be presented for the THS 2.2, CC and SA arms.

The change from baseline will be calculated for both scores. The two scores, along with the change from baseline will be summarized. The answers to the individual questions, along with the two scores and changes from baseline will be listed.

The profiles of the raw means from baseline to Day 5 for the total scores will be produced.

The analysis will compare each post baseline timepoint for the two scores. A repeated measures ANCOVA model will be used with terms for baseline score, sex, average daily CC consumption over the last 4 weeks as reported during screening, product, time-point, and the interaction between product and time-point. No adjustment will be made for multiple comparisons.

The SAS code will be the same as described in Section 12.6.3.1.1 “Urge-to-Smoke Questionnaire of Smoking Urges Brief”.

LS means for each product along with the difference (THS 2.2 - CC) and (THS 2.2 – SA) with 95% CI will be presented in the tables. The SAS code above will also be amended appropriately to obtain the right comparisons.

All figures, summaries and analyses will be performed on the FAS.

The data will be presented in the below outputs, the TFL number refers to the TFL number in the accompanying TFL shell document:

TFL number	Title
FIGURES	
15.1.2.35	MNWS Total Scores Arithmetic Mean and 95% CI– FAS
15.1.2.36	MNWS Total Scores Arithmetic Least Squares Means and 95% CI– FAS
TABLES	
15.2.4.50	Descriptive Statistics of MNWS Total Scores – FAS
15.2.4.51	Analysis of MNWS Total Scores – FAS
LISTINGS	
15.3.6.12	Listing of MNWS Questionnaire Results and Changes from Baseline

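### The repeated-measures code for QSU-brief, MCEQ and MNWS models an undefined `reduction` and requests no LS means by time point, so it does not match the analysis that the SAP text describes

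*SAP*

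**What the plan says.** **Text.** For QSU-brief, SAP 12.6.3.1.1 states: "The analysis will compare each post baseline timepoint in the domain and total scores". SAP 12.6.3.1.2 says of MCEQ: "The analysis will compare each post baseline timepoint in the subscales". SAP 12.6.3.1.3 says of MNWS: "The analysis will compare each post baseline timepoint for the two scores". The associated tables and figures are titled as analyses, LS means or LS mean differences of scores or subscales. The tables are to show LS means per product with the difference THS 2.2 - CC, and also THS 2.2 - SA for QSU-brief and MNWS.

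**Code.** The model statement in SAP 12.6.3.1.1 is "Model reduction = base_QSU sex cigarette_cons product", continued on the next line with the product-by-time interaction. The LS-means request is "Lsmean product / diff alpha=0.05 cl". MCEQ and MNWS take over this code; the MCEQ section says "The SAS code will be the same as described in Section 12.6.3.1.1".

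**Related definitions.** SAP 7 defines change from baseline as value minus baseline: "Each individual change from baseline will be calculated by subtracting the individual" subject's baseline from the later value. SAP 9 explains that the interaction was added "to enable least square means to be calculated at each time point", to explore the pattern over time, and that the main product comparison is the one over all time points.

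**The concern.** The code is presented as the code to be used, so a programmer would follow it. It departs from the text in two ways.

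- **Response.** The text and output titles concern scores; the code names `reduction`. Where the SAP does model change from baseline, for plasma nicotine and cotinine (SAP 12.6.2.2), the code says so. The different word here leaves the direction open. Higher QSU-brief scores mean more urge to smoke, and higher MCEQ scores mean greater intensity on the subscale. An unnoticed reversal would turn less urge or less satisfaction with THS 2.2 into more.
- **LS means.** The interaction is in the model, but the means that it was added to provide are not requested.

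**Working it through.** The plan states no figure for these models, so there is none to reproduce. The check compares code with text, does the algebra for the response, and confirms it on one simulated dataset.

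**Step 1. Response.** Let Y be the post-baseline score, B the baseline score (a covariate in the model), m the adjusted mean score of an arm and b the mean baseline. Suppose the fitted score model is Y = βB + (product and other terms).

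| Reading of `reduction` | Coefficient of B | THS 2.2 - CC difference | LS mean |
|---|---|---|---|
| score, Y | β | d | m |
| change, Y - B (SAP 7) | β - 1 | d | m - b |
| ordinary sense, B - Y | 1 - β | -d | b - m |

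The baseline covariate absorbs the shift by B, so only the third reading changes the difference, and it changes only the sign. Under the second and third readings the LS means are not score means, contrary to the output titles.

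**Step 2. Numerical check.** The SAP model was fitted to simulated complete data with arms of 80, 40 and 40 (SAP 6.1), Days 1 to 5 and an unstructured covariance. The effects put in are assumptions that serve only to test the algebra. The overall THS 2.2 - CC difference was:

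- score: +0.6793 (SE 0.1377)
- value minus baseline: +0.6793 (SE 0.1377)
- baseline minus value: -0.6793 (SE 0.1377)

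**Step 3. LS-means request.** `Lsmean product` gives one contrast per pair of arms, averaged over the days. A request for `product*time_point` gives the daily contrasts. On the same data (score scale) these are 1.1573, 0.8437, 0.5128, 0.5708 and 0.3121. Their mean is 3.3967 / 5 = 0.6793, which is the overall contrast. In this example the overall figure hides a difference on Day 1 more than three times that on Day 5 (1.1573 / 0.3121 = 3.7).

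**Step 4. How many results are affected.** SAP 7.3.2 to 7.3.4 give 3 QSU-brief scores (two factors and a total), 5 MCEQ subscales and 2 MNWS totals. QSU-brief and MNWS have two contrasts each; MCEQ has one, because the SA arm does not complete it after baseline.

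- Overall contrasts: 3×2 + 5×1 + 2×2 = 15
- Daily contrasts over Days 1 to 5: 15×5 = 75

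The printed code gives the 15 and none of the 75.

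**Step 5. The time main effect.** The text lists a time-point term that the code omits. This is harmless, because `product*time_point` already spans it. In the simulation every estimate and standard error was the same with and without it.

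**The case against.** A reader might infer that the reported differences will have the wrong sign. The documents do not establish that. The only baseline difference that the SAP defines is value minus baseline, which gives the same product difference as the score. The SAP also uses the word reductions loosely when it compares THS 2.2 with SA (SAP 12.6.2.1, 12.6.2.4 and 12.6.3.4), where the response is a Day 5 or Day 6 value or a change from baseline. Other printed code uses placeholders that are not valid variable names, and `reduction` may be another. This objection stands against asserting a reversal. It does not supply the missing definition.

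A reader might also infer that requesting product LS means is an error, or that the time pattern is not estimated. Neither follows. SAP 9 makes the comparison over all time points the main one, and the fitted model contains the daily effects. What is missing is the request that reports them. No output title says by day, and the table shells are in a separate document that is not available here.

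The QSU-brief and MNWS sections add that the code will be amended to obtain the right comparisons. That could be read to cover daily differences. It follows the sentence on the THS 2.2 - CC and THS 2.2 - SA differences, though, and mentions neither time points nor the response. MCEQ has no such sentence, so the gap is clearest there.

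Finally, raw mean profiles and descriptive tables of scores and changes would stand beside the model results, so a reversed sign could be noticed. This lowers the risk but does not make the code agree with the text.

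**Conclusion.** The point holds as a mismatch between code and text, and no further. The response is undefined for ten scores. A sign reversal, of full size d to -d with unchanged standard error, follows only if `reduction` means baseline minus value; under the SAP's own definition of change there is none. Under either of these readings the product LS means are not the score means that the titles announce.

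As printed, the code yields the 15 overall differences that SAP 9 calls the main comparison, but none of the 75 daily differences that the text promises. The count assumes five post-baseline days per score and the contrasts named in each section.

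The endpoints are exploratory and descriptive, with no success criterion attached. The primary biomarker analysis is not affected.

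**What to change.** In SAP 12.6.3.1.1:

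1. Replace `reduction` by the post-baseline score.
2. Keep `lsmeans product / diff cl` as the main comparison.
3. Add `lsmeans product*time_point / diff cl`, and report the within-day THS 2.2 - CC and THS 2.2 - SA differences only. With three arms and five days the request prints 15×14/2 = 105 pairs, of which 10 are needed per score.

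Use the same code for MNWS and MCEQ, with the matching baseline score as covariate and THS 2.2 - CC only for MCEQ. The time main effect may be listed to agree with the text; it changes no LS-mean difference.

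If change from baseline is preferred as the response, define it as in SAP 7 and retitle the LS-mean outputs accordingly.

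The cost is a few words of SAP code. No new data are needed.

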12.6.3.1.2 Modified Cigarette Evaluation Questionnaire

The MCEQ will be administered daily from Days -1 to 5. The baseline will be the last assessment prior to 06:29 AM on Day 1.

All summaries, profiles and analysis will be presented for the THS 2.2 and CC only. The MCEQ is not captured for the SA arm.

The change from baseline will be calculated for the five domain scores. The domain scores, along with the change from baseline will be summarized. The answers to the individual questions, along with the domain scores and changes from baseline will be listed.

The profiles of the raw means from baseline to Day 5 for the five subscale scores will be produced.

The analysis will compare each post baseline timepoint in the subscales. A repeated measures ANOVA model will be used with terms for baseline MCEQ score, sex, average daily CC consumption over the last 4 weeks as reported during screening, product, time-point, and the interaction between product and time-point. No adjustment will be made for multiple comparisons.

The SAS code will be the same as described in Section 12.6.3.1.1 “Urge-to-Smoke Questionnaire of Smoking Urges Brief”.

LS means for each product along with the difference (THS 2.2 - CC) with 95% CI will be presented in the tables.

All figures, summaries and analyses will be performed on the FAS.

The data will be presented in the below outputs, the TFL number refers to the TFL number in the accompanying TFL shell document:

TFL number	Title
FIGURES	
15.1.2.38	MCEQ Subscales Arithmetic Mean and 95% CI– FAS
15.1.2.39	MCEQ Subscales Arithmetic Least Squares Mean Differences and 95% CI – FAS
TABLES	
15.2.4.52	Descriptive Statistics of MCEQ Subscales – FAS
15.2.4.53	Analysis of MCEQ Subscales – FAS
LISTINGS	
15.3.6.13	Listing of MCEQ Questionnaire Results and Changes from Baseline

12.6.3.1.3 Minnesota Nicotine Withdrawal Questionnaire

The MNWS will be administered daily from Days 0 to 6 for the assessment of Day-1 to Day 5 as it is a 24-hour recall questionnaire. The baseline will be the last assessment prior to 06:29 AM on Day 1.

All summaries, profiles and analysis will be presented for the THS 2.2, CC and SA arms.

The change from baseline will be calculated for both scores. The two scores, along with the change from baseline will be summarized. The answers to the individual questions, along with the two scores and changes from baseline will be listed.

The profiles of the raw means from baseline to Day 5 for the total scores will be produced.

The analysis will compare each post baseline timepoint for the two scores. A repeated measures ANCOVA model will be used with terms for baseline score, sex, average daily CC consumption over the last 4 weeks as reported during screening, product, time-point, and the interaction between product and time-point. No adjustment will be made for multiple comparisons.

The SAS code will be the same as described in Section 12.6.3.1.1 “Urge-to-Smoke Questionnaire of Smoking Urges Brief”.

LS means for each product along with the difference (THS 2.2 - CC) and (THS 2.2 – SA) with 95% CI will be presented in the tables. The SAS code above will also be amended appropriately to obtain the right comparisons.

All figures, summaries and analyses will be performed on the FAS.

The data will be presented in the below outputs, the TFL number refers to the TFL number in the accompanying TFL shell document:

TFL number	Title
FIGURES	
15.1.2.35	MNWS Total Scores Arithmetic Mean and 95% CI– FAS
15.1.2.36	MNWS Total Scores Arithmetic Least Squares Means and 95% CI– FAS
TABLES	
15.2.4.50	Descriptive Statistics of MNWS Total Scores – FAS
15.2.4.51	Analysis of MNWS Total Scores – FAS
LISTINGS	
15.3.6.12	Listing of MNWS Questionnaire Results and Changes from Baseline

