7.8.3.5 Minnesota Nicotine Withdrawal Scale (revised version)

The MNWS is a valid and reliable scale that has been used previously to examine signs and symptoms of withdrawal from cigarette smoking (Hughes and Hatsukami, 1986; Hughes and Hatsukami, 2008). It consists of two scales: a 'self-report scale' and an 'observer scale'.

For the purpose of this study, only the self-reporting scale will be used and filled-in by the subject. Furthermore, the subject's weight will not be recorded for the purpose of the MNWS. At the end of the assessment of the questionnaire, the subject's pulse rate will be recorded.

Subjects will be asked to rate the items for the previous 24-hours on a scale ranging from 0 to 4 (where 0 = none, 1 = slight, 2 = mild, 3 = moderate, 4 = severe).

The MNWS (revised version) will be completed on a daily basis from Day 0 to Day 6. On each day, MNWS has to be asked prior to product use but no later than 10:00 AM.

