12.1.2 Definitions for Statistical Data Analysis

In general, baseline is the last available time-point prior to Day 1, 06:30 AM.

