7.3.4 Minnesota Nicotine Withdrawal Scale (revised edition) Questionnaire

The MNWS (Hughes and Hatsukami 2008) is a 24 hour recall that will be completed by the subject him/herself daily on Day 0 to Day 6 prior to product use to reflect the previous days experience. Therefore although it is collected on Days 0 to 6 it will be reported as Days -1 to 5. Only the self-reported part of the MNWS will be used.

The self-reported part of the MNWS consists of the following 15 items which are rated over the last 24 hours on a scale of 0 to 4 (see Table 6). Higher scores indicate greater intensity on that scale.

The total scores will be derived by summing the individual item scores if all items are non-missing, otherwise the total score will be set to missing. The first total score calculated by summing the first 9 items is based on validated items, the second score is based on 6 extra items which are thought to have an impact on withdrawal but have not been validated.

**Table 6: Minnesota Nicotine Withdrawal Scale (Revised Edition)
Questionnaire Scores**

	Question	Total Score
1	Angry, irritable, frustrated.	1 and 2
2	Anxious, nervous.	1 and 2
3	Depressed mood, sad.	1 and 2
4	Desire or craving to smoke.	1 and 2
5	Difficulty concentrating.	1 and 2
6	Increased appetite, hungry, weight gain.	1 and 2
7	Insomnia, sleep problems, awakening at night.	1 and 2
8	Restless.	1 and 2
9	Impatient.	1 and 2
10	Constipation	2
11	Dizziness	2
12	Coughing	2
13	Dreaming or nightmares	2
14	Nausea	2
15	Sore throat	2

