**Table 16: Assessment Windows**

Assessment	Nominal Time point(s)	Window
CO breath test	Day -2 and Day 6 Morning (Days -1 to 5)	Irrespective of product use To be done within 15 minutes prior to product use (for THS 2.2 and CC arms) or between 08:00 AM and 09:30 AM (SA arm)
	Day -1 to Day 5	Between 12:00 PM and 01:30 PM, 04:00 PM and 05:30 PM, and 08:00 PM and 09:30 PM
Assessment of Cough	Day 0 to 6	To be done prior to smoking/product use but not later than 10:00 AM.
MNWS Questionnaire	Day 0 to 6	To be done prior to product use but not later than 10:00 AM
QSU-brief questionnaire	Day -1 to 5	08:00 PM to 11:00 PM
MCEQ questionnaire	Day -1 to 5	08:00 PM to 11:00 PM
Nicotine and cotinine in plasma	Day 0 to Day 4 (all study arms) between 08:00 PM and 09:30 PM	
	Day 5 (THS 2.2 and CC arms) within 15 minutes before first product use (T_0): then additional blood samples at 2 hour intervals from T_0 until 11:00 PM.	Each sample has a 5 minute time window
	Day 6 (THS 2.2 and CC arms): 20 and 24 h after T_0 of Day 5 Day 5 and Day 6 (SA arm): On Day 5, between 08:00 PM and 09:30 PM. On Day 6, between 08:00 AM and 9:30 AM.	5 minute time window
COHb blood Sampling	Days -1 to 4 Morning sample on Day 5	8:00 PM to 09:30 PM Within 15 minutes prior to product use (for THS 2.2 and CC arms) or between 08:00 AM and 09:30 AM (SA arm)
	Day 5 other samples	Between 12:00 PM and 01:30 PM, 04:00 PM and 05:30 PM, and 08:00 PM and 09:30 PM

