12.1.4 Definitions for Statistical Data Analysis

The following definitions (Table 19) for statistical analyses/presentations will be used:

Table 19: Definition of terms for the statistical analysis

Term	Definition
Baseline Value	The last assessment prior to 06:29 AM on Day 1

N.B. For data where baseline is different to the above will be defined in the specific section of the SAP.

For urine collections taken on Days x to y, e.g., Days 5 to 6, these will be referred to as collected on Day x, i.e., Day 5, in the SAP.

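### The MNWS baseline is set by clock time, so a Day 1 form completed on schedule but after 06:29 AM can enter the model as post-baseline

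*SAP*

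**What the plan says.** - **Baseline.** SAP 12.6.3.1.3 sets the MNWS baseline by the clock: "The baseline will be the last assessment prior to 06:29 AM on Day 1". This repeats the default in SAP 12.1.4, "The last assessment prior to 06:29 AM on Day 1", which allows a different baseline if the relevant section defines one. Protocol 12.1.2 is similar: "In general, baseline is the last available time-point prior to Day 1, 06:30 AM".
- **Completion window.** SAP Table 16 gives the MNWS window for Days 0 to 6 as "To be done prior to product use but not later than 10:00 AM". Protocol 7.8.3.5 agrees: "On each day, MNWS has to be asked prior to product use but no later than 10:00 AM". Protocol Table 10 repeats this for Day 1.
- **Recall and labelling.** The form covers the previous 24 hours. SAP 7.3.4 moves the label back one day: "Therefore although it is collected on Days 0 to 6 it will be reported as Days -1 to 5". The form collected on Day 1 is therefore reported as Day 0. SAP 6.1 has all subjects on their own CC through Day 0.
- **Analysis.** SAP 12.6.3.1.3 fits a repeated-measures model to the post-baseline time points, with the baseline score as covariate and a product-by-time interaction. SAP Section 9 names the MNWS among the analyses whose main product comparison is taken over all time points. The interaction is there to give least squares (LS) means at each one.
- **Second score.** The text of SAP 7.3.4 says that "the second score is based on 6 extra items". Table 6 in the same section assigns items 1 to 9 to both scores and items 10 to 15 to score 2 only.

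**The concern.** The clock rule suits an evening form. The same sentence is used for the QSU-brief and MCEQ, which are completed between 08:00 PM and 11:00 PM, so their last form before Day 1 is the Day 0 form. The MNWS is a next-morning recall form, and its last pre-switch record is collected on Day 1, in a window that extends beyond the cut-off.

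A subject can therefore follow the schedule exactly and still lose the Day 1 form as baseline. Two things follow:

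1. The covariate recalls Day 0 for some subjects and Day -1 for others, depending on the minute of completion.
2. A record describing a CC-smoking day joins the post-baseline data and is averaged into the comparison that the SAP calls the main one.

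Lateness could also differ by arm. In the THS 2.2 and CC arms the form must precede the first product use, which is allowed from 06:30 AM. The smoking abstinence (SA) arm has no product use, so only the 10:00 AM limit applies.

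**Working it through.** The documents give no power or precision figure for the MNWS, so there is nothing to reproduce. The check follows the written rules.

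**Gap between cut-off and window.** From 06:29 AM to 10:00 AM is 600 − 389 = 211 minutes.

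**Records on each side of baseline.** Seven forms are collected (Days 0 to 6, reported as Days -1 to 5).

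| Day 1 form completed | Baseline record (reported day) | Post-baseline records (reported days) |
|---|---|---|
| Before 06:29 AM | Day 0 | Days 1 to 5 (5 records) |
| 06:29 to 10:00 AM | Day -1 | Days 0 to 5 (6 records) |

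**Effect on the pooled comparison.** The SAP's code requests LS means for product with a product-by-time term. These weight time-point levels equally, however many records each level holds. With a constant arm difference δ on Days 1 to 5 and a difference δ₀ on the extra Day 0 level:

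pooled difference = (5δ + δ₀) / 6

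If δ₀ = 0, this is 5δ/6 = 0.833δ, a loss of 1/6, or about 17%.

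**Does this need most forms to be late?** No, because the weighting is by level. A simulation used 80 THS 2.2 and 40 CC subjects, compound symmetry with correlation 0.6 (assumed), δ = 1 from Day 1 and no difference on Day 0. There were 400 runs per setting; 391 could be fitted at 10% late.

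| Day 1 forms completed late (assumed) | Mean pooled estimate, true effect 1 |
|---|---|
| 10% | 0.838 |
| 25% | 0.843 |
| 50% | 0.834 |
| 100% | 0.834 |

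**What a late form contains.** Subjects learn their arm before 06:30 AM on Day 1, when the exposure period begins. An SA form completed at 10:00 AM includes up to 3.5 hours of abstinence in its 24-hour recall, or 3.5/24 ≈ 15% of the period. For THS 2.2 versus SA, δ₀ may therefore not be exactly zero. Any difference in the same direction as δ makes the loss smaller than 1/6.

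**Second score.** Items run from 0 to 4. Score 1 is 9 × 4 = 36 at most. Score 2 is 15 × 4 = 60 at most by Table 6, and 6 × 4 = 24 if the sentence is taken to mean only the added items.

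**The case against.** The strongest reply is that the intended baseline is visible. SAP 7.3.4 relabels the forms, and SAP 12.6.3.1.3 itself says that they assess Day -1 to Day 5. By reported day, the last record before Day 1 is Day 0. A programmer working from reported days would choose it and meet no problem; the 06:29 AM sentence looks like repeated general text. This is a fair account of likely intent. But the MNWS section restates the clock rule rather than making an exception, and no passage overrides it.

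The second reply is that the clock rule protects something. A late Day 1 form is completed after the arm is known and, in the SA arm, possibly after abstinence has begun. The Day 0 form, recalling Day -1, is also a CC-smoking record and precedes disclosure, so it is a usable baseline. This stands, and the fix has to allow for it. It does not justify counting reported Day 0 as post-baseline.

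A reader might also infer more than the documents support:

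- **That most subjects lose the Day 1 form as baseline.** No completion times are given. 10:00 AM is an outer limit, and in two arms the form must precede product use, which may start at 06:30 AM.
- **That the MNWS results will be 17% too small.** This requires the literal reading, late forms coded as a sixth level, a constant effect and no arm difference on that level. The LS means for Days 1 to 5 are not averaged with Day 0, and an added Day 0 level would be visible in the output.
- **That score 2 is undefined.** Table 6 is explicit item by item, and the added items read naturally as additional to the first nine.

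**Conclusion.** The point holds as a defect in a written rule for an exploratory endpoint. Followed literally, SAP 12.6.3.1.3 lets an on-schedule Day 1 form become a post-baseline record of a day on which all arms smoked CC, and that record enters the pooled comparison. The illustrative size is retention of about 5/6 of a constant effect, under the assumptions above. The actual size depends on completion times and coding, which the documents do not give.

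The score 2 wording is a minor inconsistency that Table 6 largely settles in favour of the 15-item sum (0 to 60).

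The primary analysis and the success criterion do not use the MNWS and are unaffected.

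**What to change.** In SAP 12.6.3.1.3, replace the clock rule with a day-based one, for example: *MNWS baseline is the record reported as Day 0, that is, the form collected on the morning of Day 1 before product use; post-baseline time points are reported Days 1 to 5.* SAP 12.1.4 already provides for section-specific baselines.

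The small downside is that some baseline values will be recorded after arm disclosure and, in the SA arm, may include up to about 3.5 hours of abstinence. Either flag forms completed after 06:29 AM on Day 1, or add a sensitivity analysis with the reported Day -1 form as baseline for everyone. Under either choice, reported Day 0 must not count as post-baseline.

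In SAP 7.3.4, amend the text so that score 2 is the sum of all 15 items (0 to 60), as in Table 6.

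The cost is two edited SAP sentences and, if chosen, one further run of the same model. Data collection does not change.
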